2. SYNOPSIS

| | |
|--|--|
| Name of Sponsor/Company: Clearside Biomedical, Inc. | |
| Name of Investigational Product: Triamcinolone Acetonide (CLS-TA) Injectable Suspension | |
| Name of Active Ingredient: Triamcinolone Acetonide | |
| Title of Study: MAGNOLIA: Multi-Center, Non-Interventional Extension Study of the Safety and Efficacy of CLS-TA for the Treatment of Macular Edema associated with Non-Infectious Uveitis | |
| Study center(s): Multi-Center | |
| Principal Investigator: Multi-Center | |
| Studied period: 6 Month Duration Estimated date first patient enrolled: October 2016 Estimated date last patient completed: September 2017 | Phase of development: Non-interventional study |
| Objectives: Primary: Demonstrate the maintenance of efficacy of CLS-TA, up to 6 months following exit from Parent study, as shown by the need for additional therapy or the increase in maintenance therapy, for the symptoms of uveitis. Secondary: Determine the maintenance of safety of CLS-TA up to 6 months following exit from Parent study, as demonstrated by incidence of adverse events related to Parent study investigational product | |
| Number of patients (planned): approximately 30 | |
| Diagnosis and main criteria for inclusion: Participation in CLS1001-301, non-infectious uveitis Phase 3 (Parent) study without additional therapy for uveitis | |
| Investigational product, dosage and mode of administration: No investigational product administered in this study | |
| Reference therapy, dosage and mode of administration: None | |
| Criteria for evaluation: Efficacy: Mean time to additional uveitis therapy or change in maintenance therapy for uveitis Safety: Incidence of Adverse Events and serious adverse events grouped by organ system, relatedness to Parent study investigational product, and severity | |
| Statistical methods: All data collected in the study database will be presented in the listings. Listings will include change from baseline. Baseline is the Crossover Visit. Time to Rescue Therapy will be analyzed using Kaplan-Meier analysis including 95% confidence intervals, log rank p-value for difference between treatments, and quartiles. | |

4. LIST OF ABBREVIATIONS

The following abbreviations and specialist terms are used in this study protocol.

Table 2: Abbreviations and Specialist Terms

| Abbreviation or Specialist Term | Explanation |
|--|---|
| AE | Adverse Event |
| BCVA | Best Corrected Visual Acuity |
| CRF | Case Report Form |
| CST | Central Subfield Thickness |
| ETDRS | Early Treatment of Diabetic Retinopathy Study |
| GCP | Good Clinical Practice |
| ICH | International Conference on Harmonization |
| IEC | Institutional Ethics Committee |
| IOP | Intraocular Pressure |
| IRB | Institutional Review Board |
| IND | Investigational New Drug |
| ITT | Intent-to-Treat |
| IVT | Intravitreal |
| MedDRA | Medical Dictionary for Regulatory Activities |
| NSAID | Non-Steroidal Anti-Inflammatory Drug |
| OCT | Optical Coherence Tomography |
| PP | Per Protocol |
| SAE | Serious Adverse Event |
| SCS | Suprachoroidal Space |
| SD-OCT | Spectral-Domain Optical Coherence Tomography |
| TA | Triamcinolone Acetonide |
| VEGF | Vascular Endothelial Growth Factor |

5. INTRODUCTION

5.1 Disease Background

Uveitis is the fifth most common cause of visual loss in the developed world ([Goldstein 2009](#); [Wood 2011](#); [Miserocchi 2013](#)). Significant vision loss can occur in up to 35% of children and adults, and uveitis accounts for 5% - 20% of legal blindness in both the United States and Europe, and perhaps as much as 25% of blindness in the developing world ([Rothova 1996](#); [Bodaghi 2001](#)).

There are a number of causes associated with this vision loss including cataract formation or progression, chorioretinal scarring, retinal detachment, and secondary glaucoma, but the dominant cause of vision loss within uveitis comes from chronic macular edema accounting for about one third of visual impairment or blindness ([Wood, 2011](#); [Dick, 1994](#); [Karim, 2013](#)). Approximately 30% of all uveitis patients and up to 60% of intermediate- and pan-uveitis patients experience macular edema ([Lardenoye, 2006](#)).

5.2 Scientific Rationale

All subjects entering this trial will have received either CLS-TA or sham procedure from the Parent study, CLS1001-301, as masked investigational product. The objective of the Parent study is to evaluate the safety and efficacy of suprachoroidally administered CLS-TA for the treatment of macular edema associated with non-infectious uveitis. Two doses of CLS-TA or a sham procedure will be performed in the Parent study on each subject enrolled at Day 0 and Month 3 visits and the primary endpoint will be evaluated 6 months following the enrollment.

In addition to providing a robust efficacy and improved safety profile over currently used corticosteroid delivery methods, suprachoroidal administration of precisely delivered local corticosteroid therapy may provide a longer cessation of uveitis symptoms and reduced steroid sensitivity. This potential benefit will be evaluated in this extension study of non-infectious uveitis patients who participated in the Parent study and who have not received additional therapy for uveitis.

5.3 Description of Investigational Product

All subjects entering this trial will have received either CLS-TA or sham procedure from the Parent study, CLS1001-301, as masked investigational product. There will be no investigational product in this study.

Additional information regarding CLS-TA is available in the Investigator's Brochure.

5.4 Summary of Clinical Experience

TA has been safely and effectively used in human ocular therapeutics to treat ocular conditions involving inflammation for over 50 years. The initial recommended dose of the TA formulation (Triesence®) approved by the FDA for ocular indications is 4 mg in 100 µL.

Clearside is developing CLS-TA, a proprietary TA formulation for the treatment of non-infectious uveitis by administration to the SCS.

The completed clinical study, CLS1001-101, was a Phase 1/2, open-label, safety and tolerability study in subjects with intermediate-, posterior-, or pan- non-infectious uveitis. Each subject received a single suprachoroidal injection of 4 mg in 100 µL TA (Triesence). Nine (9) of the 11 subjects in the safety analysis set (82%) completed the 26-week study. All subjects had at least one AE, with a total of 37 AEs reported. One serious event (unrelated pulmonary emboli; SAE) occurred. No deaths were reported. No significant increases in IOP were reported. The most commonly reported AE, eye pain, was reported in 4 subjects.

The completed clinical study, CLS1001-201, is a Phase 2, randomized, masked safety and efficacy study in subjects with macular edema associated with non-infectious uveitis. Twenty-two subjects were randomized to either a single suprachoroidal injection of CLS-TA, 4 mg in 100 µL or 0.8 mg in 100 µL. Subjects in the 4.0mg treatment arm were observed to have a mean reduction in central subfield of thickness (CST) of 164 microns (p=0.002) when measured from baseline at 2 months. No subjects discontinued due to Adverse Event and there were no investigator-reported increases in IOP at follow-up visits.

Additional information regarding clinical experience with TA administered to the SCS, is available in the Investigator's Brochure.

6. TRIAL OBJECTIVES AND PURPOSE

The purpose of this study is to characterize the continued clinical benefit(s) regarding safety and efficacy of suprachoroidally administered CLS-TA, triamcinolone acetonide injectable suspension, for the treatment of macular edema associated with non-infectious uveitis. This study will be a non-interventional extension of the Parent study, CLS1001-301.

6.1. Primary Objective

Demonstrate the maintenance of efficacy of CLS-TA, up to 6 months following exit from Parent study, as shown by the need for additional therapy or the increase in maintenance therapy, for the symptoms of uveitis.

6.2. Secondary Objectives

Determine the maintenance of safety of CLS-TA up to 6 months following exit from Parent study, as demonstrated by incidence of adverse events related to Parent study investigational product

7. INVESTIGATIONAL PLAN

7.1. Overall Study Design

This is a non-interventional extension study of up to 6 months for subjects completing the Parent study. The Parent study is a Phase 3, multicenter study to assess the safety and efficacy of 4 mg of CLS-TA administered via suprachoroidal injection compared to a sham procedure in the treatment of subjects with macular edema associated with non-infectious uveitis.

The study design of the Extension study includes 4 clinic visits over a maximum of 24 weeks. Subject eligibility will be established at Visit 1 during the crossover day from the Parent study to the extension study (Day 0). Follow-up visits will be conducted every 6 weeks up to 24 weeks (Visit 4). At Visit 4, subjects will have a final evaluation conducted 24 weeks following study entry (48 weeks from Parent study randomization). Parent study masking will remain in effect until the Parent study is unmasked.

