8.3. Subject Withdrawal Criteria

Subjects may withdraw from the study at any time and for any reason without obligation. Subjects may be removed from the study at the Investigator's discretion or if they require Rescue due to disease progression that warrants further treatment.

If a subject withdraws from the study or if the Investigator removes a subject from the study, the Investigator should make every attempt to complete all Visit 4 assessments ([Section 20.1. - Appendix A](#)). If at any time during the study a subject is considered at immediate risk for a vision-threatening event due to study participation, the subject should be treated as soon as necessary, with the investigator determining appropriate care or additional therapy ([Section 9.2.2.](#)).

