9.2.2. Additional Treatment

If at any time during the study a subject is considered at immediate risk for a vision-threatening event, the Investigator should immediately follow best medical practice in the Investigator's judgment for treating the subject. All additional therapy will be recorded in the subject's medical chart and the CRF.

Rescue Criteria

If at any time during the study any of the following criteria are met in the study eye, the use of a treatment should be introduced. The therapy implemented is left to the discretion of the Investigator.

- A loss of 10 or more ETDRS BCVA letters due to uveitis from either of the previous two visits
- CSF > 320 μ m OR an increase in CST of \geq 100 microns or 20%, whichever is lower, from either of the previous two visits
- In the investigator's medical judgement, the uveitic complications in the study eye have worsened and the condition needs to be addressed

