9.4. Randomization and Blinding

While there will be no randomization in this non-interventional extension study, the masking from the Parent study will be protected in this trial until the Parent study has completed and is appropriately unmasked.

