11.2. Central Subfield Thickness as Measured by SD-OCT

Retinal thickness and disease characterization will be assessed at every visit via spectral domain optical coherence tomography (SD-OCT) (Heidelberg SPECTRALIS® or Zeiss Cirrus™). The SD-OCT instrument and technician must be certified prior to enrolling any subjects. The technician is encouraged to use the same certified photography equipment throughout the subject's study participation. All photos should be taken by the same photographer, whenever possible, on each subject per research site. Images will be sent to a central reading facility for analysis and interpretation in a masked fashion.

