20. APPENDICES

20.1. Appendix A: Schedule of Assessments

| Assessment | Crossover ¹ | Extension Study Visit | | | | Early Termination |
|---|------------------------|-----------------------|---------|---------|---------|-------------------|
| | | Week 24 | Week 30 | Week 36 | Week 42 | |
| Parent Study | Week 24 | Week 30 | Week 36 | Week 42 | Week 48 | |
| Extension Study | Day 0 | Week 6 | Week 12 | Week 18 | Week 24 | |
| Informed Consent | X | | | | | |
| Inclusion/ Exclusion | X | | | | | |
| Assess AEs | X | X | X | X | X | X |
| Con Med Review | X | X | X | X | X | X |
| BCVA ² | X | X | X | X | X | X |
| Slit lamp Biomicroscopy ^{2,3} | X | X | X | X | X | X |
| IOP ² | X | X | X | X | X | X |
| Dilated Indirect Ophthalmoscopy ² | X | X | X | X | X | X |
| SD-OCT ² | X | X | X | X | X | X |

1 Same as parent study Week 24 visit. Ensure these procedures are completed. Do not repeat if done in parent study.

2 All ophthalmic assessments should be completed for the study eye only

3 Any finding of cataract should be graded

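### Masking ends when the Parent study is unmasked, not when the extension ends, so site judgements could be biased if assignments reach sites within 24 weeks of the last crossover

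*Combined protocol and SAP*

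**What the plan says.** Two places in the protocol set the end of masking. Section 7.1 states that "Parent study masking will remain in effect until the Parent study is unmasked". Section 9.4 states that "the masking from the Parent study will be protected in this trial until the Parent study has completed and is appropriately unmasked". Neither refers to the last extension visit or to extension database lock.

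Extension Day 0 is the crossover visit, which footnote 1 of Appendix A describes as "Same as parent study Week 24 visit". Follow-up then runs to extension Week 24, which is Parent Week 48 (section 7.1).

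The primary endpoint is time to rescue therapy (13.5.1). It is analysed by Kaplan-Meier with a log-rank p-value between the Parent arms (13.5.2). Section 9.2.2 lists the rescue criteria. One is pure judgement: "In the investigator's medical judgement, the uveitic complications in the study eye have worsened and the condition needs to be addressed". Another is numeric but carries an attribution: "A loss of 10 or more ETDRS BCVA letters due to uveitis from either of the previous two visits". Once any criterion is met, "the use of a treatment should be introduced". Section 8.3 adds that "Subjects may be removed from the study at the Investigator's discretion", and section 12.3 leaves adverse event causality to the investigator.

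Two masking safeguards are stated. On OCT, section 11.2 says that "Images will be sent to a central reading facility for analysis and interpretation in a masked fashion". Section 12.5.2 has expedited reports sent to investigators without the arm.

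**The concern.** The Parent endpoint falls at 6 months (5.2), the same point at which subjects enter the extension. The Parent study can therefore complete and be unmasked while extension subjects are still in follow-up, and the rule as written would then no longer protect the extension.

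Rescue is a physician's act. An investigator who knows that a subject had sham may treat sooner, and one who knows that a subject had CLS-TA may wait. Either would separate the late part of the curves with no true difference between arms. Discretionary removal and related/not-related calls are open to the same influence, and the causality calls feed the secondary objective (6.2). Bias of this kind cannot be reliably undone afterwards.

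**Working it through.** The plan gives no figure of its own to reproduce: the sample size of about 30 rests on clinical considerations (13.2). What can be checked is the calendar and, under stated assumptions, the possible size of the bias.

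**Calendar.** 24 + 24 = 48 weeks and 4 × 6 = 24 weeks, so the exposed period after each crossover is 24 weeks. The synopsis expects the first subject in October 2016 and the last to complete in September 2017. If the last completer reaches Week 24 (168 days), the last crossover falls between 17 March and 15 April 2017. The entry window W is then at most 28.0 weeks (1 October 2016 to 15 April 2017) and at least 19.6 weeks (31 October 2016 to 17 March 2017).

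**Assumptions, none of them given in the documents.** Entry is uniform. The lag L runs from the last crossover to release of assignments to sites. A share p = 0.5 is rescued by Week 24 at a constant hazard h = −ln(0.5)/24 = 0.0289 per week, and rescued subjects exit (9.3). Half of rescue is discretionary (d = 0.5). After release, only that half shifts, by a factor k = 2 or 3 between the arms, with sham treated sooner:

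- sham hazard × [(1−d) + d√k] = 1.207 (k = 2) or 1.366 (k = 3)
- CLS-TA hazard × [(1−d) + d/√k] = 0.854 or 0.789

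**Rescues after release.** The share is [(e^(−hL) − 0.5)/h − 0.5(24−L)]/(pW). For L = 4 and W = 28: (0.8909 − 0.5)/0.0289 = 13.54; 13.54 − 10 = 3.54; 3.54/14 = 25%, or 3.8 of 15 rescues.

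**Spurious Week 24 gap.** With v the time from release to Week 24, the gap is (0.5/W) times the integral, over v from 0 to 24−L, of e^(hv(1−m)) for CLS-TA minus the same for sham, where m is the arm's multiplier. For L = 4, W = 28, k = 2 the integrals are 20.87 and 18.85, so the gap is 0.5 × 2.02/28 = 3.6 points.

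**Hazard ratio.** This is the large-sample Cox value, CLS-TA/sham, by numerical integration. The plan does not report a hazard ratio; it is shown only for scale.

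Each gap and ratio is given for k = 2 to k = 3:

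| Lag (weeks) | Rescues after release, of 15 (W = 28 / 19.6) | Gap in points, W = 28 | Gap in points, W = 19.6 | Hazard ratio, W = 28 | Hazard ratio, W = 19.6 |
|--|--|--|--|--|--|
| 4 | 3.8 / 5.4 | 3.6–5.8 | 5.2–8.3 | 0.92–0.87 | 0.88–0.82 |
| 8 | 2.3 / 3.3 | 2.3–3.7 | 3.3–5.3 | 0.95–0.92 | 0.93–0.88 |
| 12 | 1.3 / 1.8 | 1.3–2.1 | 1.9–3.0 | 0.97–0.95 | 0.96–0.94 |
| 16 | 0.5 / 0.8 | 0.6–0.9 | 0.8–1.3 | 0.99–0.98 | 0.98–0.97 |
| 20 | 0.1 / 0.2 | 0.1–0.2 | 0.2–0.3 | above 0.99 | above 0.99 |
| 24 or more | 0 | 0 | 0 | 1 | 1 |

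**Against sampling error.** With 15 per arm and 50% rescued, the standard error of the Week 24 difference is √(2 × 0.25/15) = 0.18, or 18 points. The standard error of the log hazard ratio with 15 events is about 2/√15 = 0.52. The largest bias in the table, −ln(0.82) = 0.20, is about 0.4 of that.

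**False-positive rate.** Simulated log-rank tests (40,000 trials, 15 per arm, lags of 4 to 12 weeks) reject in 5.2% to 7.0% of trials, against 5.1% with no shift. If all rescue were discretionary, the range is 5.4% to 12.0%.

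**The case against.** The strongest reply is that the documents show a missing safeguard and not a planned disclosure. Section 9.4 requires the Parent study to have completed and to be appropriately unmasked. Parent subjects who do not cross over may finish later than the last crossover, and unmasking a study need not mean sending individual assignments to sites. The Parent protocol, which may govern this, is not available here. A reader might infer from section 7.1 that sites will be told partway through the extension; the documents do not say so. This part of the reply stands, and it is why the concern is conditional and why lags of 16 and 20 weeks, where almost nothing happens, belong in the table.

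A reader might also infer that rescue and OCT are unprotected, or that the log-rank result would be seriously inflated. Neither follows. OCT reading is central and masked, expedited reports hide the arm, and the numeric visual acuity and thickness triggers leave less room because treatment is expected once they are met. The larger error rates need all rescue to be discretionary, which those triggers make implausible.

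The model is also simple: constant hazards although visits are six-weekly, one rescue rate for the bias, equal arms in the simulation, and no estimate for causality calls. It shows scale and does not predict.

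What does not stand is that these safeguards close the gap. None governs judgement-based rescue, the attribution of visual acuity loss to uveitis, removal or causality once sites know the arm.

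**Conclusion.** The gap in the text is real: masking is tied to the Parent study, and nothing extends it to the end of the extension. Whether it does harm depends on two facts that the documents do not give: when individual assignments are released and to whom. There is no effect if sites are not told, or are told 24 weeks or more after the last crossover.

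Under the stated assumptions, the harm at short lags is a modest shift in the estimate in favour of CLS-TA, fading to almost nothing by 20 weeks. It is small beside the study's own imprecision, and inflation of the false-positive rate is small. Severity is minor to moderate. It is worth fixing because the change is cheap and the bias could not be repaired later.

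**What to change.** In sections 7.1 and 9.4, replace the end of masking with wording such as:

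> Individual Parent assignments will not be released to subjects, investigators, site staff, site monitors or others who conduct or assess the extension until extension database lock, even if the Parent study is unmasked earlier for its own analysis and reporting. Expedited-report handling (12.5.2) and individual unmasking for subject safety are unchanged.

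This restricts only release to people working on the extension. It does not regulate how the Parent study is analysed or reported.

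Finalise the extension's statistical analysis plan before Parent unmasking; section 13 at present requires only that it precede database lock.

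Record the date of any earlier release to a site. If one occurs before that site's last subject exits, add a supportive Kaplan-Meier and log-rank analysis that censors the site's subjects at that date. In simulation this keeps rejection at 4.9% to 5.3% for lags of 0 to 12 weeks, provided that release dates are independent of outcome.

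The cost is protocol wording, an access list and a date record, with no change to visits or treatment. The downside is that sites and subjects learn assignments later, by up to about 24 weeks plus time to lock. The supportive analysis, if needed, loses events: at lags of 4, 8 and 12 weeks it keeps 11.2, 12.7 and 13.8 of 15 with 28-week entry, and 9.6, 11.7 and 13.2 with 19.6-week entry.

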7.2. Number of Subjects

The study population will include approximately 30 adult subjects that successfully complete the Parent study without requiring additional therapy to treat symptoms for uveitis as defined by the protocol. The expected duration of participation in the study is up to 24 weeks from study entry. The complete inclusion and exclusion criteria are presented below in Section 8.

7.3. Treatment Assignment

This is a non-interventional extension study. There will be no investigational product administered in this study.

7.4. Criteria for Study Termination

The study or parts of the study may be discontinued by the Sponsor, or at the recommendation of an Investigator after consultation with Sponsor, at any time.

If the clinical study is prematurely terminated or suspended, the Sponsor will inform the Investigators and the regulatory authorities of the termination/suspension and the reason(s) for the termination/suspension. The Investigator should promptly notify the IEC/IRB of the termination or suspension and of the reasons.

8. SELECTION AND WITHDRAWAL OF SUBJECTS

8.1. Subject Inclusion Criteria

Subjects are eligible for participation in this study if s/he meets all of the following criteria:

1. Enrolled in the Parent study, CLS1001-301, through Visit 8/Month 6
2. Willing and able to provide written informed consent prior to any study procedures; willing to comply with the instructions and attend all scheduled study visits

